For study activities that involve contact with participants via telephone or video, study team members will only contact Veterans from a private area so no one outside of the study team can overhear the conversation or have access to research information or protected health information. The study team member that conducts a study activity via telephone or video will obtain the address of the Veteran's location where they will participate and the contact information of a person at or near the Veteran's location who can be called in the case of emergency. If there is not a person at or near the Veteran's location available in case of emergency, the study team member will notify the Veteran that they will call 911 if there is an emergency and provide the 911 dispatch with the Veteran's address. Veterans will participate via phone or video only if they have a safe, private location from which to participate. No phone or video contact will be recorded in any way.

Benefits

Subjects may benefit from HIV screens as well as medical laboratory tests. Those findings may be helpful in their clinical care if the patients wish the data to be shared with their clinicians. The study is not intended to directly benefit the subjects. As an indirect benefit to the subjects and others, the study may enhance collaboration between hepatology, substance use treatment, and mental health providers to bring about a higher level of coordinated patient care and substance use treatment. Collectively, these potential benefits outweigh the relatively small risks associated with filling out study questionnaires, submitting blood, saliva, and urine samples, and participating in neuroimaging assessments.

Protected Health Information

The date that biological specimens are collected, processed, and/or stored will be listed on the storage containers (e.g., cryovials) utilized for this study. This identifier is used for quality control purposes in order to track specimens and monitor sample integrity/viability. The PHI to be collected is the minimum necessary needed to conduct the research and can't be further reduced.

The purpose of the data collected regarding drug abuse, alcoholism, alcohol abuse, and infection with HIV is to conduct scientific research, and no personnel involved in the study will identify, directly or indirectly, any individual patient or subject in any report of such research (e.g. manuscript or publication).

Multi-Site Study Concerns

Determining VA from Non-VA Research

This study will take place both at the Portland VA and at OHSU. VA Research will include consent, screening, breathalyzer and/or saliva alcohol testing, interviews, questionnaires, blood draws, oral fluid collection, urinalyses, and x-rays. Non-VA Research will include the MRI scans acquired at OHSU's Advanced Imaging Research Center (AIRC) Address: [name]; [contact]. In addition, some statistical analyses for this project will be performed by the Biostatistics and Design Program at OHSU. All data sent to OHSU for statistical analysis will be coded.

Costs To Subjects

None of the participants will pay for any of the procedures or visits in this study because they are only for research study purposes.

Subject Compensation

Subjects will be reimbursed \$125 for the initial visits (\$75 for visit 1 and \$50 for visit 2). Subjects who participate in the 6-month follow up visits will receive an additional \$125 (\$75 for visit 3 and \$50 for visit 4). In sum, subjects can earn \$250 total if they complete all of the scheduled visits. Payment will be

provided in the form of electronic fund transfer (EFT) into the Veteran's bank account. This compensation is reasonable and commensurate with the expected contributions of the participant. The amount of payment and terms of the payment are described in the informed consent form. Payments are fair and appropriate and do not constitute (or appear to constitute) undue pressure or influence on, or coercion of, the prospective research subjects to volunteer for or continue participation in the research study.

Privacy and Confidentiality

All study data derived from subject procedures will be obtained specifically for research purposes. Research records will be maintained according to the VA research records retention schedule. Data will be stored in a manner intended to preserve patient confidentiality. Hard-copy protected health information (PHI) (e.g., collected from clinical interviews and neuropsychiatric study visit procedures) will be stored in locked cabinets in the PIs VA office and laboratory space. Electronic PHI will be stored on servers behind the VA firewall accessed by password-protected VA computers. Each subject is assigned a unique identifier (study ID) based on a study identifier and number (i.e., DAA-xxx). Only coded or de-identified data, not PHI, are used for analysis. The file linking the study ID to the patient's name will be stored in a separate password-protected file on a secure server behind the VA firewall. Coded data will be stored on OHSU's REDCap application, a highly secure and robust web-based research data collection and management system. No identifiable information will be entered into this application at any time. The statisticians will not have access to the code or PHI at any time. The spreadsheet linking the code to the subject will remain behind the VA firewall at VAPORHCS. Once the study has ended, the link will be stored by the VAPORHCS Research & Development Service.

DTI and MRI images will be collected at the AIRC at OHSU. No PHI is used to identify subjects and only the subject's coded ID is entered at the time of the scan. The raw data for each scan are downloaded to the [name] Lab (Co-I) Linux workstations in Building 100, room 5C-107 or Building 103, room E-141 at the VAPORHCS. Image analysis will take place on these workstations in VA space. The primary storage location for the coded neuroimages will be on a password-protected network drive at the OHSU Advanced Computing Center (ACC), to which only the research team has access. Study personnel will also analyze coded neuroimages using the ACC Exacloud System, a shared server which executes specific analysis scripts without removing data from its secure network drive.

Additionally, to complete image analysis remotely, study personnel will utilize an OHSU computer that is connected to the virtual private network (VPN) per OHSU ITG. This allows computers connected remotely to access the OHSU network and utilize network resources, including remote access of other network computers, while still having the same security level as being on campus. Using remote access software (TeamViewer, putty, etc.) for Linux workstations or MobaXterm software for accessing the ACC Exacloud System, study personnel will conduct image analyses remotely.

As participants are seen within clinical spaces for research visits, and to ensure that participants are in the right area for study visits, participants will check-in with front desk staff/MSAs of the appropriate clinic. Study staff will send appropriate MSAs an encrypted e-mail with participant name, date, and time of study visit to allow MSAs to perform normal clinical duties and assist participants in being routed to study staff.

Certificate of Confidentiality

To further protect subject's privacy and confidentiality, the investigators will obtain a Certificate of Confidentiality from the National Institute of Health. With this Certificate, the investigators cannot be forced (for example by court subpoena) to disclose information that may identify subject's in any federal, state, or local civil, criminal, administrative, legislative, or other proceedings.

Information and/or Specimen Management

Blood specimens are collected from human subjects by study personnel or the VA phlebotomy lab specifically for research purposes. Specimens are coded with the subjects' unique identifiers and the date that the samples are processed or stored. The unique identifier matches the subjects' coded neuropsychiatric and demographic data. To track frozen sample storage, a hand-written log is maintained and secured in [name] laboratory. An electronic record is additionally created. Together with research staff, [name] maintains viable samples by monitoring freezer temperatures and ventilation, tracking specimen identification and location, and training staff involved in any aspect of the process.

Clinical and laboratory data collected from consenting participants will be contributed into an existing IRB-approved VA Liver Disease repository ([name], PI, IRB #3891). Contribution to the repository is required, as stated in the informed consent form and the HIPAA authorization.

Transfer of Data Ownership

N/A

Data and Safety Monitoring Plan (DSMP)

Monitoring human participant recruitment, biological specimen collection, neuropsychiatric data collection, neuroimaging assessments, and data entry will be performed by the PI and study staff that performs the study visits and procedures. Any adverse events will be reported immediately to the PI and [name] (Co-I; Responsible Clinician) who will evaluate the patient and determine if any additional evaluation or treatment is needed. [name] will ensure that adverse events are properly reported to the IRB. The study staff will examine all cumulative adverse events quarterly to determine if there are any systematic problems.

Study staff is trained on the protocols to ensure that procedures are being conducted within the scope of the approved protocols. [name] [name], a licensed psychologist and neuropsychologist, trains and supervises the clinical research staff in the administration and scoring of neuropsychological tests and psychological measures. [name], a psychiatrist and expert in neuroimaging, trains and supervises the research staff in neuroimaging procedures and data analysis. Recruitment and enrollment for clinical projects are reviewed regularly at [name] weekly laboratory meetings with research staff and at monthly meetings with [name] (Co-I). At these meetings, research staff provides enrollment updates, and the research team problem solves recruitment issues to ensure that projected enrollment numbers are obtained. The PI checks procedures (at least monthly) to verify that they are being conducted per the approved protocol, including the responsibilities and roles for gathering and monitoring data. The data are recorded by research staff as it is collected, and data accuracy is verified by double scoring, data entry and visual verification.

References & Literature Cited

ANAND, B. S., CURRIE, S., DIEPERINK, E., BINI, E. J., SHEN, H., HO, S. B., WRIGHT, T. & GROUP, V.-H.-S. 2006. Alcohol use and treatment of hepatitis C virus: results of a national multicenter study. *Gastroenterology*, 130, 1607-16.

ARGYROPOULOS, S. V., PLOUBIDIS, G. B., WRIGHT, T. S., PALM, M. E., HOOD, S. D., NASH, J. R., TAYLOR, A. C., FORSHALL, S. W., ANDERSON, I. M., NUTT, D. J. & POTOSKAR, J. P. 2007. Development and validation of the Generalized Anxiety Disorder Inventory (GADI). *J Psychopharmacol*, 21, 145-52.

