VA

U.S. Department of Veterans Affairs

Veterans Health Administration
VA Portland Health Care System

Research & Development Service
[name]
Mail code: R&D 16
[name]

[contact], [name]
[contact]

[contact]
[contact]
www.ohsu.edu/pniresearch

Summary results for ClinicalTrials.gov

Title: NURA-007-17F, HCV and co-morbid alcohol use disorder: a translational investigation of antiviral therapy outcomes on CNS function

NCT number: NCT03902366

Document date: October 30, 2024

Thank you for the opportunity to conduct this research study.

Please contact me with any questions.

Sincerely,

A handwritten signature in black ink, appearing to read "[name]".

[name].
Principal investigator

Research Protocol

Title

HCV and Co-morbid Alcohol Use Disorders: A Translational Investigation of Antiviral Therapy Outcomes on CNS Function

Investigators

Principal Investigator: [name].

Responsible Clinician: [name].

Specific Aims/Purpose

The primary objective of this research project is to compare neuropsychiatric functioning, cortical activity, white matter integrity, and immune response among Veterans with and without alcohol use disorder (AUD), before and after direct-acting antiviral (DAA) therapy [a new treatment for chronic infection with the hepatitis C virus (HCV)]. Demographically-matched comparison groups of Veterans without HCV (HCV-, with and without AUD) will similarly be evaluated to determine the relative contribution of HCV and an HCV “cure” to outcomes putatively affected by alcohol abuse.

Two specific aims are proposed.

Aim 1: Determine the impact of DAA therapy and a sustained viral response on central nervous system (CNS) function

Aim 2: Evaluate the effects of AUD and unhealthy alcohol drinking on DAA therapy outcomes and CNS function.

The information learned will address a critical gap in our knowledge concerning the effects of alcohol use on DAA therapy outcomes and will help inform treatment guidelines that could be translated to clinical practice, such as targeted interventions to treat AUD in conjunction with HCV infection and follow-up strategies for patients who successfully complete DAA therapy but then need care for other potential CNS-related outcomes.

Central hypothesis: It is hypothesized that adults with HCV and co-morbid AUDs may be at increased risk of persistent brain dysfunction following DAA therapy.

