Specific hypotheses: *Hypotheses 1.1 and 2.1 (neuropsychiatric outcomes)*. Following DAA therapy and obtaining a sustained viral response (SVR), 1.1: participants will show improved neuropsychiatric outcomes (e.g., cognitive function, fatigue, mood), as compared to baseline (pre-DAA therapy). 2.1: participants without AUDs will show greater improvement in neuropsychiatric outcomes than participants with AUDs. *Hypothesis 1.2 and 2.2 (neuroimaging outcomes)*. Reduced fractional anisotropy (FA) will be observed in the tracts that connect regions between which there is decreased functional connectivity. 1.2 and 2.2: Disintegrity within white matter tracks [as measured by FA and mean diffusivity (MD)] observed at baseline visits will be improved following DAA therapy, with greater improvement observed in participants without AUDs. On the fMRI Balloon analogue risk task (BART) and Monetary incentive delay task (MID), adults with HCV will be significantly more likely to display more impulsivity during the baseline visit, as compared to the post-DAA therapy visit. It is hypothesized that AUD may attenuate the positive antiviral therapy effects on impulsivity. *Hypothesis 1.3 and 2.3 (immune activation profile)*. Inflammatory profiles will be associated with neuropsychiatric impairments and alterations in white matter integrity and cortical activity. Following DAA therapy and obtaining an SVR, 1.3: participants will show reduced immune activation profiles (i.e., restored T cell phenotypes and a reduced inflammatory profile), as compared to baseline, and 2.3: participants without AUDs will show greater a reduction in inflammatory factors than participants with AUDs.

Scientific Rationale and Significance

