Alcohol withdrawal status. The Clinical Institute Withdrawal Assessment for Alcohol, revised version (CIWA-Ar) will be administered and scored at every visit. Using this scale mild alcohol withdrawal is defined with a score less than or equal to 15. For participants who score in the mild range, we will record the score and continue with the visit. For participants in the moderate (scores of 16 to 20) or severe (scores > 20) ranges, visits are discontinued and follow-up procedures are conducted, including notifying the responsible clinician ([name], Co-I). Visits that are discontinued do to moderate or severe CIWA-Ar scores will be rescheduled.

Description of neuropsychiatric study visit measures. The neuropsychiatric study visit battery was designed to assess a full range of neuropsychiatric symptoms (e.g., AUD severity, cravings, depression, anxiety, fatigue, pain) and cognitive skills (e.g., attention, memory, executive function). The cognitive domains were selected for assessment because previous research by our group and others has demonstrated that HCV is associated with impairments in these domains (Huckans et al., 2009, Huckans et al., 2011). The present study follows up on these findings by evaluating whether individuals who receive DAA therapy for HCV evidence improved psychiatric and cognitive function, and the extent to which AUDs impact outcomes. Measures were selected because of their sound psychometric properties (e.g., reliability, validity, large normative sample that can be corrected for demographics), and because they are widely used by clinicians and have established clinical utility. *The neuropsychological measures that will be repeated have equivalent versions that will be alternated across study visits to minimize practice effects.* Measures will be administered according to published standard administration procedures.

Psychiatric and substance use disorder diagnoses

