Diffusion-Weighted Imaging: DTI preprocessing will be performed using the DTI preprocess script (Takuya Hayashi, Center for Life Science Technologies, RIKEN, Kobe, JP) for FSL [(Smith et al., 2004) FMRIB, Oxford]. Scans will be corrected for eddy current distortion and motion. B_0 inhomogeneity distortion will be corrected using a B_0 field map (magnitude and phase) in FSL's fugue. DTI estimates (FA, λ_{1-3} , V_{1-3} , MD) will be calculated using DTIFIT. Voxelwise statistical analysis will be performed with TBSS (Smith et al., 2006) and nonlinear registration to the FMRIB58_FA common space will be conducted. Each subject's aligned FA data will be projected onto a mean skeleton. Voxelwise cross-subject statistics will be performed with FSL's *Randomise* with threshold-free cluster enhancement (TFCE).

Voxel-Based Morphometry: Structural images will be analyzed with FSL-VBM (Douaud et al., 2007) an optimized VBM protocol (Good et al., 2001) carried out with FSL (Smith et al., 2004). Images will be brain-extracted and tissue segmented, registered to the MNI-152 standard space using non-linear registration (Andersson et al., 2007), and flipped along the x-axis to create a left-right symmetric, study-specific gray matter template and modulated with a voxel-wise division by the Jacobian determinant of the non-linear transformation matrix to correct for local expansion or contraction. The modulated gray matter images will be smoothed with an isotropic Gaussian kernel with a sigma of 3 mm (FWHM = 7 mm). Group contrasts will be tested with FSL's *Randomise*, a permutation-based non-parametric procedure.

Statistical analyses and power. Statistical analyses for the project will be performed by the research team and the Biostatistics and Design Program at OHSU. All data sent to OHSU for statistical analysis will be coded.

Neuropsychiatric and laboratory measures. We plan to calculate the change in the response over six months between post- and pre-DAA therapy for each subject and use general linear models (GLMs) to assess whether average change differs among the four groups—either due to AUD, HCV, or the

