potential interaction of these factors—after possibly controlling for other subject-level covariates that remain constant (or nearly so) over the six months (e.g., age, sex, HCV genotype). Variables that could meaningfully vary over time (e.g., TFLB score, CIWA-Ar score) will be summarized in terms of a difference and then included as a covariate. Number of DAA therapy provider contacts will be included as an extra covariate that counts total contacts. All models will use “robust” (sandwich estimators) of variance to guard against potential misspecification of the underlying distribution of change scores or due to non-constant variance among the groups (Long and Ervin, 2000). The AUD \times HCV interaction will be assessed first in all models fit, and will be removed from the model only if evidence suggests ($p > 0.10$) these two factors don’t modify one another; otherwise, subsequent comparisons of each separate effect will be made within each level of the other (e.g., effect of HCV separately characterized for those with and then without AUD).

A supervised and directed approach will be taken in the exploratory analysis of inflammatory biomarkers. Principal component analysis (PCA) will be used to reduce the collection of ~12 correlated immune factors to a smaller number of uncorrelated linear combinations (the principal components) of biomarkers [e.g., (Bowman et al., 2012)]. Each component of this reduced set of uncorrelated patterns of inflammatory expression will be subjected to the same general linear models described earlier to determine whether AUD, HCV or AUD \times HCV are associated with it, even after adjustment for other covariates. If the overall test of association in the linear model shows significant ($p < 0.10$, for initial screen) variation among the groups, then separate models will be conducted on those biomarkers that most heavily contribute/dominate the principal component being screened. In this way, we may identify combinations of markers that are sensitive to AUD and HCV treatment outcomes, particularly CNS function.

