Power. We estimated group size using fmripower (Mumford and Nichols, 2008). The MATLAB-based program calculates a power estimate given the between-group and within-subject error terms associated with a two tailed t-test of regression coefficients. The results suggested that 30 subjects (male and female) per group would yield a power of 0.8 for the test comparison. This sample size yields an 80% chance for us to identify AUD \times HCV interaction effects of 0.91 standard deviation (SD) or larger at the 0.10 level of significance. Use of the higher alpha-level is done to lessen the chance of making a type II (overlook) error and mistakenly omitting this term from the model. We also have 80% power for a 0.05-level test to detect any main effect, for either AUD or for HCV, of at least 0.51 SD in size. **Table 2** shows the smallest average change (between post- and pre-DAA therapy) among groups that would be of practical interest and the subsequent main effects (AUD+ vs AUD-; HCV+ vs HCV-) and interactions that derive from these minimally relevant average changes. The anticipated SD for the change scores was derived from reported SDs of each outcome supported by literature, and then converted to a SD for the difference assuming a modest correlation of 0.60 between pre- and post-DAA responses within the same subject. The principal comparisons proposed in this work parallel those in our preliminary work, and we were able to readily demonstrate differences in planned comparisons between the groups. Therefore, the proposed 30 subjects per group should provide us with sufficient power to test the predictions, anticipating that a small number of participants with HCV may not achieve SVR (n = ~3-6).

Table 2. Statistical power to evaluate antiviral therapy outcomes of significant clinical impact

Response/outcome	SD(diff)	Treatment group ^a			Effects and Power ^b			
		AUD-/HCV-	AUD-/HCV+	AUD+/HC V-	AUD+/HCV+	AUD main	HCV main	Interact.
Cognitive performance^c								
Attention	2.25	3.5	3.7	1.2	3.5	-1.25 (0.85)	1.25 (0.85)	2.1 (0.81)
Memory	2.50	3.0	3.4	0.4	3.0	-1.50 (0.91)	1.50 (0.91)	2.2 (0.78)
Executive function	1.80	2.0	2.1	0.3	2.0	-0.90 (0.78)	0.90 (0.78)	1.6 (0.78)
Behavioral response								
Impulsivity (BART/MID) ^d	1.35	0	-0.2	-0.1	-1.5	-0.70 (0.80)	-0.80 (0.90)	-1.20 (0.78)
Alcohol use (TLFB)	18.9	0	-1.0	-18	-36	-26.5 (0.99)	-9.50 (0.78)	-17.0 (0.79)
Mental health								
Depression (BDI)	4.0	0	-3.5	-2.7	-11.0	-5.1 (0.99)	-5.9 (0.99)	-4.8 (0.94)

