Expected outcomes and alternative considerations. Results are expected to determine the extent of improvement in CNS function (including neuropsychiatric outcomes) that is gained by successful completion of DAA therapy and whether or not co-morbid AUDs affect HCV treatment outcomes. Our hypotheses would be supported by finding improved CNS function following successful completion of DAA therapy (*i.e.*, obtaining an SVR), including: i) increased FA in the tracts that previously connected regions between which there was decreased functional connectivity, ii) improved functional connectivity, iii) reduced impulsivity, and iv) improved cognitive abilities. Following DAA therapy, these changes in CNS function will be associated with reduced peripheral immune activation. Individuals with active AUDs and HCV may show attenuated benefits in CNS function and immune response, post-DAA therapy. In participants with HCV and co-morbid AUDs, cumulative disruptions in cerebral connectivity that result from anatomical disruptions may contribute to persistent cognitive deficits and elevated inflammatory profiles. Alternatively, it is possible that floor effects for some of the variables (e.g., BDI-II scores) may limit our ability to detect significant improvements. However, cognitive performance benefits have been reported following IFN-based therapy for HCV (Kraus et al., 2013, Kuhn et al., 2017), and we have observed improvements in depression and fatigue in patients who obtained SVR (Huckans et al., 2015). It is also possible that differences in the number of DAA therapy provider visits between participants in the HCV+ and HCV- groups may affect neuropsychiatric outcome variables (e.g., alcohol use behavior). To assess the impact of this potential confound, we plan to include that characteristic as an extra covariate. Because CNS recovery may continue beyond the SVR assessment timepoint, patients who agree to participate in the study will be asked to allow our research team permission (via the informed consent process) to contact them for future follow-up investigation, which is beyond the scope of this current protocol. We also considered the potential concern that there may be a lack of research participants with HCV (given the pace at which the VA is treating HCV); however, estimates indicate that by 2020, there will still be ~560,000 adults with HCV in the US (Chhatwal et al., 2016).

Table 3. Project timeline

Year 1	Year 2	Year 3	Year 4

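### Hypothesis 1.1 is worded as improvement from baseline, a standard that untreated HCV- groups would also meet on Table 2's figures; the planned HCV contrast should be named as the deciding test

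*Combined protocol and SAP*

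**What the plan says.** Aim 1 (Specific Aims/Purpose) is to determine the impact of DAA therapy and SVR on CNS function. The hypotheses state the comparison as follows.

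- Hypothesis 1.1, after therapy and SVR: "participants will show improved neuropsychiatric outcomes (e.g., cognitive function, fatigue, mood), as compared to baseline (pre-DAA therapy".
- Hypothesis 1.3: "participants will show reduced immune activation profiles (i.e., restored T cell phenotypes and a reduced inflammatory profile), as compared to baseline".
- The impulsivity part of 1.2 compares adults with HCV at baseline with the same adults after therapy.
- Expected outcomes and alternative considerations: "Our hypotheses would be supported by finding improved CNS function following successful completion of DAA therapy".

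None of these sentences mentions the HCV- groups. Elsewhere the plan relies on them. The Specific Aims say that they "will similarly be evaluated to determine the relative contribution of HCV and an HCV “cure” to outcomes putatively affected by alcohol abuse". For neuropsychiatric and laboratory measures, Statistical analyses and power will "use general linear models (GLMs) to assess whether average change differs among the four groups", with AUD, HCV and their interaction as factors. The interaction is dropped if p > 0.10. Otherwise each factor is examined within levels of the other, for example the "effect of HCV separately characterized for those with and then without AUD".

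On repeat testing, the description of the study visit measures says that the repeated cognitive tests "have equivalent versions that will be alternated across study visits to minimize practice effects".

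**The concern.** Improvement from one's own baseline attributes to DAA everything that happens over six months: any effect of viral clearance, but also repeat testing, regression to the mean, changes in drinking and natural course. The HCV- groups were enrolled to separate these, but the wording by which Aim 1 would be judged does not use them. Table 2 itself gives non-zero improvement to some untreated groups. Read literally, Hypothesis 1.1 could therefore be reported as supported with no DAA effect. At stake is which result the investigators may call support for Aim 1: the change within HCV+, or the difference in change between HCV+ and HCV-.

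**Working it through.** **Inputs.** Table 2 gives SD(diff) and then mean change for AUD-/HCV-, AUD-/HCV+, AUD+/HCV- and AUD+/HCV+. The first row reads "Attention 2.25 3.5 3.7 1.2 3.5". The others used are memory 2.50; 3.0, 3.4, 0.4, 3.0; executive function 1.80; 2.0, 2.1, 0.3, 2.0; BDI 4.0; 0, -3.5, -2.7, -11.0; FSS 0.63; 0, -1.1, -0.8, -1.3. There are 30 per group. Alpha is 0.05 for main effects and 0.10 for the interaction; tests are taken as two-sided.

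**Step 1: reproduce the plan's HCV main effect.** Effect = half of [(AUD-/HCV+ + AUD+/HCV+) - (AUD-/HCV- + AUD+/HCV-)]; SE = SD × √(2/60).

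| Domain | Effect | SE | Power (normal / t, 116 df) | Table 2 |
|---|---|---|---|---|
| Attention | (3.7 + 3.5 - 3.5 - 1.2)/2 = 1.25 | 0.411 | 0.861 / 0.855 | 0.85 |
| Memory | (3.4 + 3.0 - 3.0 - 0.4)/2 = 1.50 | 0.456 | 0.908 / 0.903 | 0.91 |
| Executive | (2.1 + 2.0 - 2.0 - 0.3)/2 = 0.90 | 0.329 | 0.782 / 0.775 | 0.78 |

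The plan's figures reproduce, so the HCV contrast that Table 2 powers is one that subtracts the control change.

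**Step 2: apply the baseline-only wording to untreated groups.** t = mean change / (SD/√30), 29 df, alpha 0.05.

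| Untreated group | Outcome | t | Power |
|---|---|---|---|
| AUD-/HCV- | Attention | 3.5/0.411 = 8.5 | >0.999 |
| AUD-/HCV- | Memory | 3.0/0.456 = 6.6 | >0.999 |
| AUD-/HCV- | Executive | 2.0/0.329 = 6.1 | >0.999 |
| AUD+/HCV- | Attention | 1.2/0.411 = 2.9 | 0.81 |
| AUD+/HCV- | Memory | 0.4/0.456 = 0.9 | 0.14 |
| AUD+/HCV- | Executive | 0.3/0.329 = 0.9 | 0.14 |
| AUD+/HCV- | BDI | 2.7/0.730 = 3.7 | 0.95 |
| AUD+/HCV- | FSS | 0.8/0.115 = 7.0 | >0.99 |

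BDI and FSS in AUD-/HCV- are set at 0, so rejection there stays at 5%.

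**Step 3: untreated change as a share of the treated change.**
- Cognition, AUD-: 3.5/3.7 = 95%, 3.0/3.4 = 88%, 2.0/2.1 = 95%.
- Cognition, AUD+: 1.2/3.5 = 34%, 0.4/3.0 = 13%, 0.3/2.0 = 15%.
- AUD+, mood and fatigue: BDI 2.7/11.0 = 25%; FSS 0.8/1.3 = 62%.

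**Step 4: HCV+ minus HCV- within AUD level.** SE = SD × √(2/30), 58 df, alpha 0.05.
- AUD-, cognition: 0.2, 0.4 and 0.1 points; power 0.063, 0.094 and 0.055.
- AUD+, cognition: 2.3, 2.6 and 1.7 points; power 0.97, 0.98 and 0.95.
- BDI: -3.5 in AUD- (power 0.92) and -8.3 in AUD+ (>0.99).
- FSS: -1.1 in AUD- (>0.99) and -0.5 in AUD+ (0.86).

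**Step 5: Hypothesis 1.3 and impulsivity.** In the HCV- groups Table 2 sets immune-factor change at 0 and +2.5 (the latter against the hypothesis), T-cell change at 0, and impulsivity at 0 and -0.1. No untreated group is projected to improve materially on these.

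**The case against.** The strongest reply is that the plan contains no pre-post test. The specified analysis for neuropsychiatric and laboratory measures is the four-group model for change, its HCV contrast already subtracts the control change, and Table 2 powers that contrast. The t values in Step 2 belong to a test that nobody has planned. The support statement sits in a narrative section, and the same section treats unequal provider visits between HCV+ and HCV- as a possible confounder, which makes sense only if the groups are to be compared. All of this stands. A reader might infer that the trial lacks a controlled analysis, or that retest gain alone would lead it to claim a DAA benefit; the documents do not support either inference.

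Two other strong readings also fail. One is that uninfected controls in general are expected to gain almost as much cognitively: this is true of AUD-/HCV- but not of AUD+/HCV-. The other is that the control gain is a practice effect. The plan does not state a cause, alternate forms are used, and Table 2's entries are labelled as minimally meaningful changes, although its power figures are built on them.

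What the reply does not remove is that hypothesis and analysis ask different questions. The model's HCV contrast does not test Hypothesis 1.1 as worded, and no sentence says that this contrast decides Aim 1.

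**Conclusion.** The concern holds as a mismatch between the stated hypotheses and the planned analysis. For Hypothesis 1.1 it has numerical force: each kind of outcome it gives as an example would meet the baseline-only wording in at least one untreated group, namely cognition in AUD-/HCV- and mood and fatigue in AUD+/HCV-. Among AUD- participants a cognitive gain from baseline would say almost nothing about DAA, because Table 2 leaves only 0.1 to 0.4 points to the HCV contrast. For 1.3 and the impulsivity part of 1.2, the point is one of wording only.

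The sizes rest on Table 2's mean changes and on one SD per outcome common to all groups, with 30 completers per group and no covariate adjustment. They do not depend on why the controls improve.

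**What to change.** State that Hypothesis 1.1 and, for consistency, 1.3 and the impulsivity part of 1.2 are supported only if the planned model's HCV+ minus HCV- difference in change favours HCV+. Use the HCV main effect when the AUD × HCV interaction is dropped, and the contrast within each AUD level when it is retained, as the analysis section already provides. Align the support statement under Expected outcomes and alternative considerations, and report change from baseline within HCV+ as descriptive.

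The contrast should not be required within AUD levels in every case. That would conflict with the plan's interaction rule and replace a 60-versus-60 comparison with two of 30 versus 30.

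The edit needs no new data or analysis. Its cost is that Aim 1 becomes harder to support than by a pre-post comparison. The pooled cognitive contrast keeps its stated power of 0.85, 0.91 and 0.78. If the interaction is retained, the AUD- cognitive contrast has only about 6-9% power, against 0.95-0.98 in AUD+. Retention is the likelier outcome on Table 2's own figures, which give the cognitive interactions 0.78-0.81 power at the 0.10 level. The protocol should acknowledge this when it restates the hypothesis.
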